## 7 Safety Analyses

The planned timing of safety reviews is described in section 2. An overview of the safety data collection is provided in [Appendix C](#).

**Analysis cohort:** Safety analyses will be carried out on participants who received a complete or partial infusion of the investigational agent (modified intention-to-treat [mITT]), unless otherwise stated.

A comprehensive safety review includes:

- Comparison of the treatment groups for the primary safety endpoint, its components, and analyses of secondary safety outcomes (described in this section)
- Analyses of infusion-related reactions and symptoms, described in section 6
- Evaluation of the “efficacy outcomes” (the pulmonary and pulmonary+ ordinal outcomes early in follow-up, and time to sustained recovery), which contain important safety information.

In addition to the full DSMB reviews, more frequent, shorter safety reports may be provided to the DSMB, for example, weekly safety reports early in the trial.

This section describes the primary safety outcome, and the analyses of AEs, SAEs, UPs, SUSARs, and deaths. Comparisons between treatment groups will be stratified by study pharmacy and by disease severity at study entry (as described in section 3 under “stratification”).

In order to streamline the reporting of events, it was decided that certain protocol-specified exempt events (PSEE) are *not reported as SAEs*, unless they are considered related to the study treatment by the investigator. The events are listed in [Appendix B](#); their composite is referred to as *clinical organ failure or serious infections*. While the *clinical organ failure or serious infection* events are serious events like SAEs, these events are reported not on the SAE eCRF unless they are considered related to the study treatment, but are reported as study endpoints on various other eCRFs.

The following safety and tolerability outcomes will be analyzed. If sample size permits, models will be stratified by disease severity and study site pharmacy, as described in section 3 under “stratification”, unless noted otherwise.

- The **primary safety endpoint** is a composite of incident grade 3 or 4 clinical adverse events, SAEs, clinical organ failure or serious infections, or death through **Day 5**. The number and proportion of participants experiencing one of these events up through Day 5 will be tabulated, and treatment groups will be compared using a CMH test stratified by study site pharmacy and by disease severity at study entry.
  - Mortality will be analyzed as a key secondary outcome, see below.
  - The individual components of the composite outcome will be summarized.
  - *Sensitivity analyses*: For interim analyses, while the trial is still enrolling, treatment groups will also be compared for time to event through Day 5 using a log-rank test, stratified by site pharmacy and disease severity at study entry; the HR will be estimated with a 95% CI using a Cox proportional hazards model, and the cumulative proportion of participants with events over the first 5 days in each treatment group will be estimated using Kaplan-Meier curves.

**Comment:** For investigational agents that are administered as a one-time infusion, such as nMAbs, the composite outcome at Day 5 is the primary measure to assess safety while the trial is still enrolling, as described in the protocol. This safety outcome and other safety outcomes through Day 28 will be considered along with the ordinal outcomes at Day 5 at interim data reviews by the DSMB to assess futility. When a trial is unblinded after the Day 90 follow-up is completed, however, treatment comparisons through Day 90 provide a more comprehensive evaluation of the investigational agent. For the publication of the main results for a specific agent, “time to death” and the composite of “death, SAE, clinical organ failure, or serious infections” through Day 90 would usually be presented as the main safety analyses, along with other safety outcomes. This decision will be agent-specific, and will be specified prior to the unblinding of the data for the agent.

- **All-cause mortality** through follow-up will be analyzed using time-to-event methods. Cumulative proportions of participants who died in each treatment group will be estimated using Kaplan-Meier estimates, and summarized in tables (proportion of participants who died by Days 5, 7, 14, 28, 60, 90, month 6, 12, and 18) and figures (Kaplan-Meier curves with pointwise 95% CIs). Treatment groups will be compared for time to death using log-rank tests, stratified by study site pharmacy and disease severity, and an overall HR will be

estimated with 95% CIs using stratified Cox proportional hazards models. Two other analyses will also be carried out to investigate the pattern of mortality differences, if any, between the treatment groups: 1) the proportional hazards assumption will be investigated; and 2) hazard ratios during the first 28 days of follow-up versus after 28 days will be estimated and compared.

- Cause of death will be MedDRA® coded and summarized by treatment group.
- The following composite endpoints will be analyzed using time-to-event methods (cumulative proportions of participants with events will be estimated using Kaplan-Meier curves with pointwise 95% CIs; treatment groups will be compared using log-rank tests; numbers and percent of participants with events will be summarized by treatment group, and overall HRs with 95% CI will be estimated using Cox proportional hazards models):
  - Composite of incident grade 3 or 4 clinical adverse events, SAEs, clinical organ failure or serious infection, or death through Day 28
    - Components of the composite endpoint will be also be summarized, overall and by system organ class. Proportions of participants who experienced any of these events by Day 28 will be compared using stratified CMH tests or logistic regression.
  - Composite of SAEs, clinical organ failure, serious infection, or death through Day 28 and Day 90
  - Composite of hospital re-admission or death through 18 months
- Treatment groups will be compared for the incidence of non-pulmonary events in the pulmonary+ ordinal outcome that are not part of the pulmonary outcome, through Day 5 and Day 7 (using time-to-event methods, with death as competing risk). These events are shown in red in [Appendix A](#).
- AEs, SAEs, and UPs will be classified by MedDRA® system organ class. AEs will be graded for severity according to the *DAIDS AE Grading Table*. Grade 1-4 clinical AEs will be reported at baseline (Day 0 prior to infusion of the investigational agent), Day 0 after the infusion, Days 1-7, and on Days 14 and 28.

The number and percent of participants with AEs will be summarized by day (Day 0 separately prior and after the infusion) and grade, and by system organ class and grade. Comparisons between treatment groups will be for the proportion of participants with AEs of a given grade or higher (i.e., any grade, grade 2+, grade 3+, grade 4). The treatment comparisons will be performed using stratified CMH tests or logistic regression.

- For comparisons by day, the proportion of participants with any grade AEs will be compared for Days 0 (after infusion) through 7, and on Days 14 and 28.
- For comparisons by grade, the proportion of participants who experienced any grade AEs (grade 2+ AEs, etc.) between Day 0 (after the infusion) through Day 7 will be compared.
- For the comparison by system organ class, CMH tests will be performed if the number of participants with AEs is sufficiently large. System organ classes may be split up into MedDRA® preferred terms (PT) for system organ classes where the treatment difference is significant.

Other clinically meaningful AE groupings (beyond system organ class) may be developed by the study team, who are blinded to the treatment effect.

- In addition to any grade AEs through Day 7, grade 3 and 4 clinical AEs are being reported through Day 28. The number and percent of participants with incident grade 3 or 4 AEs through Day 28 will be summarized, overall and by system organ class, and compared between treatment groups using stratified CMH tests. (A grade 3 or 4 AE is considered “incident” if the event was not present at baseline or increased to grade 3 or 4 from grades 1 or 2.)

To illustrate the time course, the incidence of *grade 3 or 4 AEs or death* through Day 28 will be summarized by treatment group using Kaplan-Meier estimates of the cumulative incidence functions (CIF).

- Infusion-related reactions and symptoms during infusion or within 2 hours after infusion of the investigational agent or placebo, and infusion cessation prior to completion will be tabulated and compared between treatment groups; analyses are described in section 6.
- Treatment groups will be compared for the proportion of participants who developed *organ failure or serious infections* through Day 28 and through Day 90, overall and by individual components, using stratified CMH tests. Individual components of this composite outcome will be tabulated.
- Treatment groups will be compared for incidence of organ failure, serious infections, or death through Day 28 and through Day 90, using Cox proportional hazards models; cumulative incidence functions will be estimated using Kaplan-Meier estimates.
- Treatment groups will be compared for incidence of a composite of fatal and non-fatal cardiovascular and thromboembolic events, a subset of the organ failure outcome (items 6b1, 6e2, 6e3, and 6f2 in [Appendix B](#)). Treatment groups will be compared using Cox proportional hazards models; cumulative proportions of participants with such events will be estimated using Kaplan-Meier estimates.

**Comment:** Death for causes other than cardiovascular or thromboembolic events is a competing risk. As sensitivity analysis, the treatment groups will be compared using Aalen-Johansen estimates for the cumulative incidence functions and Fine-Gray models to estimate the sub-hazard ratio (investigational agent versus placebo) for the composite outcome. If results differ substantially from the Cox regression and Kaplan-Meier estimates, mortality for reasons other than CVD and thromboembolic events will be investigated in detail.

- Treatment groups will be compared for **new requirements of dialysis**, overall and in subgroups by eGFR level (<30 mL/min versus  $\geq$ 30 mL/min at study entry), and subgroups by nAb status at study entry (nAb negative or positive).

**Motivation:** In a joint analysis of data from the first three agents studied in TICO (bamlanivimab, sotrovimab, and BRII 196/198), the incidence of dialysis was elevated in the active treatment group compared with placebo (18 versus 2 events, HR=5.7 [95% CI: 1.2-24.6]). This safety signal was seen only among those who were nAb seronegative at study entry (16 events in the active arms versus 2 placebo, HR=5.0 [95% CI: 1.1 to 22.0]),

while only 2 events occurred among those who were nAb seropositive at study entry, both in the active arms. The mean time from enrollment to needing dialysis was 21 days.

**Comment:** Of the 20 participants with “incident dialysis”, 2 had required dialysis prior to their COVID-19, and thus may be mis-classified for treatment-emergent dialysis. Both had eGFR < 10 mL/min at study entry and thus were at high risk for dialysis, and both had been allocated to active treatment.

**Hypothesis:** The incidence of dialysis is elevated with nMAb treatment compared with placebo, in particular among those with eGFR < 30 mL/min, and among those who are nAb seronegative at study entry.

- Treatment groups will be compared for mean changes in laboratory test values from baseline to Day 5, and for incidence of grade 3 and 4 laboratory abnormalities at Day 5 (new abnormality or increase in grade). Laboratory tests are conducted locally, and include serum creatinine, AST/SGOT or ALT/SGPT, WBC, hemoglobin, platelet counts, lymphocyte counts, and C-reactive protein. Statistical methods are described in section 3.
- Participants who are pregnant are not eligible for enrolment. For participants who become pregnant, pregnancy outcomes will be summarized.
- In addition to the safety outcomes specified in the platform protocol, other targeted safety outcomes for specific investigational agents may be specified in appendices to the protocol. Analyses will be specified in the corresponding agent-specific appendix to this SAP.

Listings of SAEs, clinical organ failure and serious infections, incident grade 3 and 4 AEs, UPs, SUSARs, and deaths (with cause of death) by treatment group will be provided at each DSMB meeting, with new events highlighted. The listings will include important baseline characteristics, such as age, sex, and disease severity (pulmonary outcome category) at study entry.

Further safety assessments may be considered.

Corticosteroid use will be monitored; concomitant medication use is collected at baseline and at Day 5.

- Corticosteroid use (any use at baseline or Day 5) will be summarized by treatment group and by oxygen requirement (worst category through Day 5: no supplemental oxygen, < 4 L/min, conventional supplemental oxygen  $\geq$  4 L/min, high-flow oxygen or mechanical ventilation/ECMO).
- Corticosteroid use on Day 5 will be summarized by treatment group and by oxygen requirement (worst category on Day 5, as above).

The impact of study arm on composite safety outcomes and their components at day 5, 28 and 90 will be assessed for subgroups defined by baseline characteristics, including SARS-CoV-2 antibody serostatus, antigen levels, demographics, duration of symptoms at enrollment, baseline classification of “home”, clinical history and presentation (including disease severity stratum and pulmonary+ ordinal outcome at baseline). Tests for homogeneity of the treatment effect across subgroups will be carried out.

Outcomes and methods for subgroup analyses are described in detail in section 9.

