### Censoring for time-to-event analyses

For **interim** analyses, the type of censoring used will depend on the data collection schedule.

- If the reporting of the endpoint is data-driven (e.g., SAEs and deaths are reported as they occur), then follow-up is censored at the administrative censoring date, at the date of withdrawal, or loss to follow-up, whichever occurs earliest.
- If the date of the event is elicited retrospectively at fixed study visits spaced more than one week apart (e.g., “sustained recovery”), follow-up will be censored at the last day the endpoint status was ascertained.
- Sensitivity analyses will be provided for key analyses when the outcome status is uncertain.

For **final** analyses, follow-up will be censored on the last day the outcome status was ascertained.

**Adverse events** (AEs) will be classified by system organ class according to MedDRA® (currently version 24.1 [September 2021] is used; when new versions are implemented, items are recoded). AEs will be graded according to the *DAIDS Table for Grading the Severity of Adult and Pediatric Adverse Events, Corrected Version 2.1* (July 2017) (also referred to as the *DAIDS AE Grading Table*). Cause of death will also be coded according to MedDRA®.

The number and percent of participants with grade 1-4 AEs will be summarized by day and grade, and by MedDRA® System Organ Class and grade. The percentage of participants with AEs will be compared between treatment groups according to grade cut-offs, e.g., “percent of participants with any AE”, “percent of participants with grade 2 or higher AEs”, etc., using CMH tests. The total number of events and median (IQR) of events per participant will also be summarized.

Additionally, the incidence of grade 3 and higher AEs will be summarized (number and percent of participants), and compared between treatment groups using time-to-event methods.

**Significance level, two-sided tests:** Unless noted otherwise, statistical tests and confidence intervals will be 2-sided, confidence intervals will have approximate 95% coverage probability, and test results with P-values  $\leq 0.05$  will be considered “significant”. Percentages will be reported to at least one decimal place. P-values will be given to 2 significant figures.

**Cut-date for interim reviews:** Analysis data sets will be frozen (locked) several days (or weeks) prior to the review date, to allow the unblinded statisticians time to prepare a consistent

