## 6 Administration of Study Treatment

These data are an important part of the safety review, with particular emphasis on infusion-related reactions and symptoms occurring during or within up to 2 hours after the infusion. These reactions and symptoms will be graded according to the DAIDS AE Grading Table.

The administration of study treatment is also an essential element of study conduct. Several summaries, pooled across treatment groups, will be included in the open report or provided to study leadership. Any summaries of adverse events or infusion-related reactions are restricted to the closed report.

**For investigational agents administered as a one-time infusion**, the following statistics will be used to summarize the infusion in each treatment group (active and control):

- Number and percentage of participants receiving complete infusion, partial infusion, infusion paused but resumed for complete infusion, or not infused (comparison by intention-to-treat).
- Number and percentage of participants with infusion-related reactions and symptoms (reported during the infusion or within 2 hours after the infusion), by grade. (Closed report only)
- Number and percentage of participants with an incident AE, SAE, UP or SUSAR on Day 0 during or after the infusion, overall and by oxygen requirement category at time of infusion (oxygen requirement at baseline, unless updated information is available; categories: no supplemental oxygen, < 4 L/min, conventional supplemental oxygen  $\geq$  4 L/min, high-flow oxygen or mechanical ventilation/ECMO). Types of AEs will be summarized by system organ class and by grade. (Closed report only)

- Number and percentage of participants who received:
  - Prior to infusion, medication to prevent infusion reactions, and type of medication
  - During or within 2 hours after infusion, medication to treat infusion reactions, and type of medication (Closed report only)
- Among participants infused, the day of infusion (same day as randomization, next day, > 1 day after randomization), and time between randomization and beginning of infusion (median hours, IQR).
- Among participants receiving full infusion, duration of infusion (median minutes, IQR).
- Time from vial puncture (beginning of preparation of the study agent by the pharmacist) to the end of the infusion, and number and percent of participants for whom the agent-specific time window was exceeded.
- Remdesivir:

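### The any-grade and grade 2+ adverse event comparisons count symptoms already present before infusion, which dilutes, and may hide, a difference in new low-grade events after the infusion day

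*SAP*

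**What the plan says.** **Collection.** SAP section 7 provides for a pre-infusion record: "Grade 1-4 clinical AEs will be reported at baseline (Day 0 prior to infusion of the investigational agent"), followed by Day 0 after infusion, Days 1 to 7, and Days 14 and 28. The schedule in SAP Appendix D likewise lists clinical AEs of any grade on those days.

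**Comparison by grade.** Section 7 compares "the proportion of participants who experienced any grade AEs (grade 2+ AEs, etc.) between Day 0 (after the infusion) through Day 7". Section 3 gives the general rule: "The percentage of participants with AEs will be compared between treatment groups according to grade cut-offs". Neither sentence requires the event to be new.

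**Comparison by day.** Section 7: "the proportion of participants with any grade AEs will be compared for Days 0 (after infusion) through 7, and on Days 14 and 28". This has no such requirement either.

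**Comparison by system organ class.** CMH tests are planned where numbers allow. That bullet states no time window and no new-event requirement.

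**Method.** "The treatment comparisons will be performed using stratified CMH tests or logistic regression". No term for pre-infusion AEs is named.

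**Where baseline is used.** A grade 3 or 4 AE is incident "if the event was not present at baseline or increased to grade 3 or 4 from grades 1 or 2". Laboratory abnormalities are compared "for incidence of grade 3 and 4 laboratory abnormalities at Day 5 (new abnormality or increase in grade"). Section 6 reports the "Number and percentage of participants with an incident AE, SAE, UP or SUSAR on Day 0 during or after the infusion", but only for the infusion day, and it does not define incident for grades 1 and 2.

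**The concern.** Everyone enrolled is a hospitalized adult with COVID-19 symptoms. SAP section 10.2.2 lists the baseline categories when enrolment is restricted to disease severity stratum 1. The mildest is pulmonary+ category 2, which Appendix A defines as symptomatic and unable to carry out usual activities. Many participants can therefore be expected to have a grade 1 or 2 AE on record before infusion, and some of those will persist to Day 1 or later. Each such participant meets the by-grade criterion whether or not anything new happens.

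Two things follow. First, a participant who already counts because of a persisting symptom cannot count again for a new event, so the difference between arms in new events shrinks. Second, if the agent speeds the resolution of COVID-19 symptoms, fewer participants on it have a persisting AE. That would show as fewer AEs and could offset a true excess of new reactions. What is at stake is the tolerability profile at grades 1 and 2 after the infusion day.

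**Working it through.** **No plan figure to reproduce.** The documents give no rate, hypothesis or power for the any-grade or grade 2+ comparison. What follows is an illustration.

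**Inputs from the SAP.** 500 participants per arm (section 1.4); two-sided tests at 0.05 (section 3).

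**Assumed inputs.** p = proportion with a new AE, 0.40 on the agent and 0.30 on placebo. b = proportion with a pre-infusion AE that persists after infusion, equal in both arms and independent of new events. Neither p nor b is in the documents, so b is varied.

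**Formulas.** The proportion counted as written is q = b + (1 − b)p. The difference between arms is therefore (1 − b)(p₁ − p₀). Power = Φ(|q₁ − q₀|/SE − 1.96), with SE = √{[q₀(1 − q₀) + q₁(1 − q₁)]/500}, unstratified.

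Worked line for new events only (b = 0): SE = √[(0.21 + 0.24)/500] = 0.0300; 0.10/0.0300 = 3.33; power = Φ(1.37) = 91.5%.

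Worked line for b = 0.5: q₁ = 0.5 + 0.5 × 0.40 = 0.70 and q₀ = 0.5 + 0.5 × 0.30 = 0.65; SE = √[(0.2275 + 0.2100)/500] = 0.0296; 0.05/0.0296 = 1.69; power = Φ(−0.27) = 39%.

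| Persisting AE (b) | Counted, agent v placebo | Difference | Power |
|---|---|---|---|
| 0 (new events only) | 40% v 30% | 10 points | 92% |
| 0.3 | 58% v 51% | 7 points | 61% |
| 0.5 | 70% v 65% | 5 points | 39% |
| 0.6 | 76% v 72% | 4 points | 30% |
| 0.7 | 82% v 79% | 3 points | 22% |

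Pooling the variance under the null moves these results by about 0.2 of a percentage point at most.

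**Other assumed new-event rates.** With 500 per arm, b = 0.6 and pooled variance, new-event rates of 10% v 20%, 20% v 30% and 30% v 40% give power of 27% to 30%, against 91% to 99% for new events alone.

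**Unequal persistence.** Suppose new AEs occur in 30% on the agent and 20% on placebo, and symptoms persist in 50% and 60% because the agent clears them faster. The counted proportions are 0.50 + 0.50 × 0.30 = 65% on the agent and 0.60 + 0.40 × 0.20 = 68% on placebo. The sign reverses. With persistence of 55% on the agent, they are 68.5% v 68%, and the 10-point excess is almost gone.

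**The case against.** **The comparison is valid between randomized arms.** Pre-infusion AEs are balanced in expectation and the type I error is intact. What is compared is the AE burden after infusion, and the SAP does not call it a count of new events. This stands. A reader might infer that the comparison is confounded by baseline or invalid; the documents do not support that.

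**No passage shows that a difference will be hidden.** The pre-infusion prevalence, the persistence rate and the new-event rate are all absent, and at 30% persistence the illustration keeps 61% power. This also stands: dilution follows from the definition when symptoms persist, but concealment is only possible. Nor does the fall in power breach a design target, because none is set for this comparison.

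**Much of the safety question is already covered.** The primary safety endpoint through Day 5 and the Day 28 composite use incident grade 3 or 4 AEs. Incident grade 3 or 4 AEs through Day 28 are compared separately, overall and by system organ class. Section 6 reports incident AEs on Day 0 and infusion reactions up to two hours after infusion. This matters for an agent given as a single infusion: protocol Appendix H1 names infusion-related and allergic or hypersensitivity reactions as the AEs of special interest. A reader might infer that the trial's main safety conclusions are at risk; they are not. What remains is mainly new grade 1 and 2 events on Days 1 to 7, and on Days 14 and 28.

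**System organ class.** That bullet gives no Day 7 window, and no calculation is made here by class or for grade 2+ separately, where the background may be lower. Splitting into preferred terms and blinded AE groupings may separate drug-type reactions from COVID-19 symptoms, but neither removes an unchanged pre-infusion event.

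**Other SAP methods.** The section 3 GEE model for longitudinal binary outcomes contrasts follow-up with baseline. Section 7, however, names CMH or logistic regression for AEs, and the GEE contrast would not count new events either.

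**Reporting rules.** The AE definitions are in section 10 of the master protocol, which is not among the documents reviewed. The SAP's day-by-day collection suggests that a continuing event is recorded on later days, but it does not say so outright.

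**Conclusion.** The point holds as a loss of sensitivity. The SAP applies a new-or-increased rule to severe clinical AEs and severe laboratory abnormalities, but not to the low-grade clinical AEs for which pre-existing symptoms are most likely. As written, the any-grade and grade 2+ comparisons, and the by-day and system-organ-class comparisons of AEs of any grade, include unchanged pre-infusion events. They also mix symptom resolution with new events.

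The absolute difference in new events shrinks by the factor (1 − b) when persistence is equal in the two arms. The power figures rest on the assumed new-event rates, on independence of new and persisting events, on an unstratified test, and on continuing events being recorded after infusion. Only the direction of the dilution follows from the SAP's wording. The change is worth making but does not bear on the primary safety conclusion.

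**What to change.** In sections 3 and 7, extend the existing rule to all grades. For the any-grade, grade 2+ and system-organ-class comparisons, count an AE only if its event term was absent from the pre-infusion record, or its grade is higher than in that record. Use the same definition for the Day 0 incident AE summary in section 6, which now leaves the term undefined for grades 1 and 2. Keep the current tables by day and by grade as descriptive summaries of AE burden.

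The cost is SAP wording and a derived variable from data already collected. Deriving it means matching each post-infusion event to the pre-infusion record by term and grade. There are two limits. The pre-infusion record is a single time point, so a fluctuating symptom absent at that moment would count as new. And an effective agent may also prevent new or worsening COVID-19 symptoms, so some mixing of benefit with AEs will remain.
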